## **Intervention**

### TENS protocol

With reference to previous studies, the dosage of 20 sessions of 60-minute TENS could provide sufficient stimulus to elicit recovery of motor function in people with chronic stroke. In the Bi-TENS group, the subjects received TENS on both paretic and non-paretic sides of the upper limbs. In the Uni-TENS group, TENS was only applied on the paretic side of the upper limb while a placebo stimulation (P-STIM) was applied on the non-paretic side. In the Placebo-TENS+TOT group, the P-STIM was applied on both sides of the upper limbs. In the Control group, the subjects did not receive any active treatment. The disposable surface electrodes were applied to stimulate the median nerve (from the carpal tunnel to flexor digitorum superficialis) and superficial radial nerve (from the extensor pollicis longus to extensor digitorum communis).

The stimulator was 120z Dual-Channel TENS Unit (ITO PHYSITHERAPY&REHABILITATION CO., LTD, Tokyo, Japan). The parameter (100 Hz, 0.2 ms square pulses, intensity barely below the motor threshold) of TENS followed our previous study (10). The P-STIM was provided by identical-looking TENS devices that electrical circuit has been disconnected.

#### TOT protocol

The TOT protocol was developed based on the guideline of stroke rehabilitation (40). Under the supervision of a well-trained research assistant with health-related discipline training, the subjects with stroke were required to complete six 10-minute training items in each session of treatment, including stretching exercises, mobilizing exercise, strengthening exercises, seated reaching tasks, dexterity training and bimanual practice. Five minutes' interval for resting was provided between each training item.

#### **Outcome Measure**

To eliminate the bias, an experienced rehabilitation therapist who was blinded to the group allocation assessed all outcome measures in a random sequence for 5 times, including baseline, mid-intervention (4th week of study), post-intervention (8th week of study), 1-month follow-up and 3-month follow-up.

#### Primary Outcome

Fugl-Meyer Assessment of upper extremity (FMA-UE)

FMA-UE was used for evaluating the upper limb motor control in people with stroke. FMA-UE showed an excellent inter-rater ( $r=0.997$ ) and test-retest ( $r=0.965$ ) reliability in people with chronic stroke. FMA-UE has 4 subsections: (1) shoulder-arm; (2) wrist; (3) hand; (4) coordination and speed. There was a total score of 66 with 33 items with ordinal scoring from 0 to 2.

## Secondary Outcome

### The Peak Torque and co-contraction ratio of Maximum Voluntary Contraction (MVC)

Peak torque and co-contraction ratio was used to assess the muscle strength and abnormal muscle activation. The raw force data and electromyography (EMG) signal was recorded by the custom-built measurement frame mounted with load cell and surface EMG, respectively. At the beginning, the subjects were seated with shoulder flexion 0°, elbow flexion 0° and wrist 0° neutral position placed in the torque measurement. The paretic hand was fixed by stripe and the forearm was fixed by G-clamp. The 2 bar-shaped electrodes were placed on flexor carpi ulnaris and extensor carpi ulnaris. During data collection, the subjects were required to perform 5 seconds isometric MVC of wrist extension/flexion, respectively. Each movement was performed 3 times. The data of the 3 trials were averaged.

The torque of the movement was the product of the force and moment arm, which is the length from the transverse crease of the wrist to the head of the 3rd metacarpal. The peak torque would be recorded by extracting the peak value of torque being produced during MVC. Excellent intra-rater reliability ranged from 0.97 to 0.98 were reported in our pilot study.

The raw EMG was rectified and filtered by a band pass filter (20-450Hz) and a notch filter (49Hz-51Hz) by Butterworth method. Then the EMG signal would be integrated. The time window beginning at 0.25 seconds before and end at 0.25 seconds after the peak torque occurred was captured to calculate the integrated EMG (iEMG) of the agonist and antagonist. The co-contraction ratio would be calculated by the following formula:

$$\text{Co-contraction Ratio} = \frac{\text{EMG}_{\text{agonist}}}{\text{EMG}_{\text{agonist}} + \text{EMG}_{\text{antagonist}}} \times 100\%$$

Good to Excellent intra-rater reliability ranged from 0.837 to 0.975 were reported in our pilot study.

## ROM of wrist and elbow

The ROM of wrist and elbow were measured by the electrogoniometer (Model SG 110; Biometrics, Gwent, UK). The electrogoniometer showed a high intra-rater ( $r=0.90-0.92$ ) reliability (44) in people with stroke. The subjects performed maximal ROM of wrist flexion/extension and elbow flexion/extension with their paretic side twice. The mean values of 2 trials were recorded.

## Action Research Arm Test (ARAT)

ARAT was an objective scale to assess the upper limb motor function. Previous study showed that ARAT showed an excellent intra-rater ( $r=0.996-0.997$ ) and inter-rater ( $r=0.989$ ) reliability in people with chronic stroke. This ordinal scale consists of 19 items with a total score of 57. The quality of the performance on each item was rated from 0 to 3.

## Jacket Test (JT)

JT was an objective scale to evaluate the upper limb motor function by completion time of dressing task, which included shoulder abduction, flexion and elbow extension and hand gripping. JT showed a good to excellent intra-rater ( $r=0.845-0.891$ ), inter-rater ( $r=1.000-1.000$ ) and test-retest ( $r=0.781-0.795$ ) reliability in people with chronic stroke. The subjects were required to put on a jacket or cardigan sweater straight on his or her shoulders, and then took it off completely for 3 trials. The completion time of the 3 trials was averaged.

## Motor Activity Log (MAL)

The MAL questionnaire was a subjective scale to assess upper limb motor function. Subjects were required to rate the amount of use (AOU) and the quality of movement (QOM) of their paretic upper limb from 0 to 5 in 30 items of ADL. MAL showed a good reliability in both components of AOU (ICC=0.79) and QOM (ICC=0.82) in people with stroke. A higher score of AOU and QOM indicated that higher usage frequency and better performance of their paretic upper limbs, respectively.

### Community Integration Measure (CIM)

The Chinese version of CIM was used to assess the community integration level. CIM showed a good test-retest reliability (ICC=0.84) in measuring the people with chronic stroke. CIM consists of 10 items, each item rated from 1 to 5, giving a score ranged from 10 to 50. A higher score indicated a higher level of community integration.

### Statistical Analysis

All the quantitative analyses were performed by the SPSS (Version 23.0, IBM, Armonk, NY). Descriptive analysis was used to summarize subjects' demographic information. One-way analysis of variance, Chi-Squared test ( $\chi^2$  test) and Kruskal-Wallis test were used to compare the baseline characteristics of the four groups as appropriate. Intention-to-treat analysis (last observation carry forward) was used. The linear mixed models (LMM) were used to compare the changes over time in variables of interest between those in the Bi-TENS+TOT group and those in the Uni-TENS+TOT group, Placebo-TENS+TOT group and Control group. The maximum likelihood estimation was used to selected the best fit model. The first-order autoregressive structure with heterogeneous variances (AR (1): heterogeneous) was used to estimate the

parameters of statistical model. The intervention effect from pre-intervention to post-intervention was analyzed by LMM. The carryover effect from post-intervention to 3-month follow-up assessment was analyzed using the same LMM method. The significant level was set at 0.05. The post-hoc analysis would be conducted by Bonferroni correction when there was an overall significant difference.

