## Methods

### Design

This study was a single-blinded randomized, placebo-controlled trial. The study was registered on ClinicalTrials.gov (NCT03112473) and conducted in our neurorehabilitation laboratory. Informed consents were obtained before the study began. The study protocol was approved by the ethics committee of the Hong Kong Polytechnic University and conducted in accordance to the Declaration of Helsinki.

As there was no previous study investigating the effect of Bi-TENS+TOT in improving the upper limb motor control in people with stroke, the effect size (Cohen's  $d=0.314$ ) used for the calculation of sample size in this study was obtained from our pilot trial. The sample size was calculated by using G\*power version 3.1.0 (Franz Faul, Universitat Kiet Germany) with  $\alpha$  of 0.05, power of 0.80, correlation among measure of 0.5 and non-sphericity correlation of 1. Ninety-six subjects were necessary to detect a significant between-group difference in the improvement of the upper limb motor control measured by FMA-UE. In accordance to our previous clinical trial, dropout rate of was assumed to be 20%, so a buffer of 24 subjects would be included. A sample size of 120 (30 per group) was used to detect the significant between-group difference finally.

The randomization was conducted by a research assistant who did not involve in the intervention and assessment after the baseline measurement. The eligible subjects were stratified into one of the four groups randomly: Bi-TENS+TOT group, Uni-TENS+TOT group, Placebo-TENS+TOT group and Control group. The stratification was conducted by the online software "Minimize". The factors of age (50-60, 60-70,>70), sex (male, female), type of stroke (ischemia, hemorrhage) and side of lesion (left, right) were balanced in the four groups. To achieve concealment, the allocation information was kept by the research assistant. Following the provision of informed consent, subjects were informed of their allocation to one of four groups, but specific group allocation remained concealed to maintain the blinding of treatment.

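### LOCF is the only missing-data rule and precedes a likelihood mixed model that does not need it; with 20% dropout planned and no sensitivity analysis, the contrasts can be biased

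*Combined protocol and SAP*

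**What the plan says.** The Statistical Analysis section handles missing data in one sentence: "Intention-to-treat analysis (last observation carry forward) was used". It states no missingness assumption, no analysis without the carried values and no sensitivity analysis.

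The same section names the main model: "The linear mixed models (LMM) were used to compare the changes over time in variables of interest". The covariance is heterogeneous AR(1). Maximum likelihood is mentioned in connection with model choice: "The maximum likelihood estimation was used to selected the best fit model". There are two analysis windows. The first runs from pre- to post-intervention. For the second, "The carryover effect from post-intervention to 3-month follow-up assessment was analyzed using the same LMM method". The testing rule is: "The post-hoc analysis would be conducted by Bonferroni correction when there was an overall significant difference".

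The Outcome Measure section sets five assessments: baseline, then "mid-intervention (4th week of study), post-intervention (8th week of study), 1-month follow-up and 3-month follow-up". The Design section expects losses: "dropout rate of was assumed to be 20%, so a buffer of 24 subjects would be included".

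**The concern.** A mixed model fitted by likelihood accepts subjects with some visits missing. Filling in is therefore not needed to analyse everyone as randomised, and LOCF adds an assumption that the model does not require: each score stays fixed from the last visit attended.

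The assumption matters most for carryover. A subject lost before week 8 has the same carried value at week 8, 1 month and 3 months. A subject lost between week 8 and 1 month carries the week-8 value forward. Both contribute a change of exactly zero, so for them maintenance of the gain is assumed and not observed.

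In the pre-to-post window, the same rule shrinks a real contrast if dropouts would have gone on changing like those who stayed. If dropout differs between arms that share a gain, it can also produce a contrast where none exists.

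**Working it through.** **Inputs from the documents.** 120 subjects, 30 per arm, 96 required, 20% dropout, correlation 0.5, d = 0.314 (Design); five visits (Outcome Measure); LOCF, mixed model, heterogeneous AR(1), two windows, overall test then Bonferroni (Statistical Analysis).

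**The plan's own figure.** Take a repeated-measures interaction F test with f = 0.314/2 = 0.157, four groups and three measurements; the last two choices of f and of three measurements are inferred, not stated. Then λ = 0.157² × 96 × 3 / (1 − 0.5) = 14.2 on 6 and 184 degrees of freedom, which gives power 0.803 at N = 96. Inflation: 96/0.80 = 120. Both figures reproduce, and the 24 extra subjects already allow for lost data.

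**Equal random dropout, dropouts following those who stay (assumed).** Let p1 to p4 be the shares lost in baseline–week 4, week 4–week 8, week 8–1 month and 1–3 months, with linear change in each window.

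- Share of a pre-to-post contrast kept by LOCF = 1 − p1 − 0.5·p2. Loss before week 4 carries no gain; loss between weeks 4 and 8 carries half.
- Share of a post-week-8 loss kept = 1 − (p1 + p2 + p3 + p4) + p4/3. Only those lost after 1 month carry any change, and they carry one third of it.

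| Timing of the 20% (p1, p2, p3, p4) | Pre-to-post kept | Follow-up kept |
|---|---|---|
| 10, 10, 0, 0% | 1 − 0.10 − 0.05 = 0.850 | 0.800 |
| 5, 5, 5, 5% | 1 − 0.05 − 0.025 = 0.925 | 0.80 + 0.017 = 0.817 |
| 0, 0, 10, 10% | 1.000 | 0.80 + 0.033 = 0.833 |

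**If a share f of dropouts really stops changing (here f is a proportion, not the effect size).** Write L = 1 − kept. The true share is 1 − f·L, so LOCF errs by (1 − f)·L and the observed-visit fit by f·L. They are equal at f = 0.5. At f = 1 the observed-visit fit overstates: 1/0.85 = 1.18 or 1/0.925 = 1.08 pre-to-post, and 1.25, 1.22 or 1.20 at follow-up.

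**Unequal dropout (assumed, not in the documents).** Take 10% against 30% lost before week 8, split evenly over the two intervals, with a shared gain of 0.8 SD. The arms keep 1 − 0.05 − 0.025 = 0.925 and 1 − 0.15 − 0.075 = 0.775. The false contrast is 0.8 × (0.925 − 0.775) = 0.12 SD.

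**Error rates by simulation** (4 × 30, heterogeneous AR(1), maximum likelihood, windows fitted separately as planned):

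| LOCF result | AR(1) correlation 0.5 | 0.9 |
|---|---|---|
| Coverage, equal random dropout | 94–96%, both windows | about 91–92% at follow-up |
| Unadjusted pairwise type I error, 10% vs 30% with shared gain | 6.5% (observed visits 4.9%) | about 13–14% |

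At 0.5, the overall test followed by Bonferroni lowers the second row to 2.0% (observed visits 1.3%) if Control does not gain, and to 1.2% (0.7%) if all arms gain. The Design section's 0.5 is a single sample-size input, not an AR(1) parameter, so both columns are assumptions.

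**Is it enough to drop LOCF inside the two windows?** Assume no true carryover contrast, 10% against 30% lost between weeks 4 and 8, and loss logistic in the week-4 score (slope 1 or 2). At correlation 0.5 the large-sample false carryover contrasts are:

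- observed-visit fit to the follow-up window alone: 0.06 to 0.09 SD;
- LOCF: 0.035 to 0.05 SD;
- likelihood using the earlier visits: about 0.

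A post-to-3-month fit leaves out everyone lost before week 8 and ignores the early scores that predict loss. Here it does worse than LOCF.

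**The case against.** The strongest defence is that no harm is shown. Dropout by arm and visit is not reported, the 10%/30% split is invented, and with equal dropout and equal gains the LOCF contrast is unbiased. The Subjects section enrols people 1 to 10 years after stroke, in whom a score that stays put after leaving the programme is credible; LOCF would then be right. Its intervals are also narrower. All of this stands, and it is why LOCF should be kept as a reported analysis. It does not justify LOCF as the only analysis, because the plan then shows one assumption with no view of how much depends on it. The narrower intervals also come partly from shrinkage and from counting carried values as data.

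A second defence is that the plan mentions maximum likelihood only for choosing the model. That is a fair reading of the sentence, but a linear mixed model is likelihood-based and uses incomplete records either way.

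A reader might go further and infer that the planned tests are invalid. The documents do not support that. With equal random dropout, null pairwise error stays at about 5–6% or below, and the larger figures need an assumed dropout imbalance. A reader might also treat 0.314 as the pairwise contrast that LOCF shrinks; the Design section gives it only as a pilot effect size for the sample-size calculation.

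**Conclusion.** The point holds as a cheap improvement. LOCF is the sole rule, is not needed for an as-randomised analysis, and builds zero change into carryover for most subjects lost. Under the stated assumptions it keeps 85–100% of a true pre-to-post contrast and 80–83% of a true loss after week 8, or creates about 0.12 SD under a 10%/30% imbalance with a shared 0.8 SD gain. The actual size and direction are unknown.

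Two limits apply. Reassurance about coverage is tied to a correlation near 0.5 and does not carry over to 0.9 at follow-up. And it is tempting to read the LOCF and observed-visit results as bounds on the truth. They bracket it only if dropouts either stop changing or follow those who stay; if dropouts lose gains already made, neither analysis covers that case.

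**What to change.** If the analysis has not been run, replace the missing-data sentence with:

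> All randomised subjects are analysed as randomised; one LMM with all five visits is fitted by maximum likelihood to all observed data, without imputation, under a missing-at-random assumption; the pre-to-post and post-to-3-month effects are contrasts from this model; LOCF is reported as a sensitivity analysis.

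The single five-visit model is part of the fix, because separate window fits do not deliver the missing-at-random claim for carryover.

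The document is largely in the past tense. If the analysis is complete, the sentence should stay as a record of what was done. The five-visit observed-data model is then reported beside the LOCF result for each outcome and labelled as added afterwards. Giving dropout by arm and visit would let readers judge the size of the problem.

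The cost is one sentence, or one extra labelled run per outcome, with the same software, covariance structure and estimation. At correlation 0.5, confidence intervals are up to about 13% wider pre-to-post and 13–21% wider at follow-up. N = 96/120 does not change.

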## **Subjects**

One hundred and twenty subjects (mean age=61.70±5.91 years) were recruited from the local self-help groups. The inclusion criteria of the subjects included: (1) were between 50 and 80 years of age; (2) had been diagnosed with stroke within 1 to 10 years; (3) had volitional control of the non-paretic arm and at least minimal antigravity movement in the paretic shoulder; (4) had at least 5 degrees in wrist extension in the antigravity position; (5) had an Abbreviated Mental Test score  $\geq 7$ . The participants were excluded if they: (1) had any additional medical, cardiovascular or orthopedic condition; (2) had contraindications to TENS, such as implant cardiac pacemaker, skin allergy; (3) had receptive dysphasia; (4) had a significant upper limb peripheral neuropathy; (5) were involved in drug studies or other clinical trials; (6) had severe shoulder, elbow, wrist or finger contractures.

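### The pre- to post-intervention mixed model states no adjustment for baseline FMA-UE or the minimisation factors; with equal SDs, baseline adjustment alone would cut that contrast's variance by 25% at correlation 0.5, 5% at 0.9

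*Combined protocol and SAP*

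**What the plan says.** The Statistical Analysis section gives the whole model description. "The linear mixed models (LMM) were used to compare the changes over time in variables of interest" between the Bi-TENS+TOT group and the other three groups, and "The intervention effect from pre-intervention to post-intervention was analyzed by LMM". The period from post-intervention to 3-month follow-up is handled by a second model of the same kind. The covariance is heterogeneous AR(1). On model choice it says "The maximum likelihood estimation was used to selected the best fit model", without listing the candidate terms. On missing data it says "Intention-to-treat analysis (last observation carry forward) was used".

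No fixed effects are listed. Baseline values are mentioned only for descriptive summaries and for comparing the groups at entry.

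Under Design, allocation used minimisation on age band and three further factors: "sex (male, female), type of stroke (ischemia, hemorrhage) and side of lesion (left, right) were balanced in the four groups". The sample-size calculation there assumes a "correlation among measure of 0.5".

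**The concern.** Because the effect runs from pre- to post-intervention, the natural reading is that the baseline score is one of the repeated responses. If each arm has its own free baseline mean, the model subtracts baseline with weight 1. With equal SDs the efficient weight is the baseline-to-post correlation, which is below 1. The change score does correct for chance imbalance, but it carries more noise than necessary.

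The four minimisation factors were judged important enough to balance at allocation, yet they do not appear in the stated analysis.

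What is at stake is precision on the primary outcome, in particular for the Bonferroni-corrected pairwise comparisons, which rest on 24 to 30 subjects per arm. The variables needed are already collected.

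**Working it through.** **Inputs.** From Design: d = 0.314, alpha 0.05, power 0.80, correlation 0.5, non-sphericity 1, N = 96 evaluable, 20% dropout, 120 in total over four arms. From Primary Outcome: test-retest r = 0.965 for FMA-UE. The number of measurements (3: baseline, mid, post) and f = d/2 = 0.157 are not stated; they are inferred because they reproduce the plan's figure.

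**1. The plan's sample size.** For a repeated-measures within-between interaction with 4 groups and 3 visits:

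- lambda = f² × N × m/(1 − rho) = 0.157² × 96 × 3/0.5 = 14.2, with df 3 × 2 = 6 and 92 × 2 = 184. Power is 0.803.
- 96/(1 − 0.20) = 120. At N = 120, power is 0.897.

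So N = 96 is reproduced without any covariate.

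**2. What the model estimates.** On complete data with free group-by-visit means, the generalised least squares contrast does not depend on the covariance structure. A numerical check (4 groups, 3 visits, heterogeneous AR(1)) gave −0.26704 for the model contrast and −0.26704 for the raw difference in change scores.

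**3. Baseline adjustment, equal SDs.** Var(change) is proportional to 2(1 − rho), and Var(post given baseline) to 1 − rho². The ratio is (1 + rho)/2.

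| rho | ratio | variance cut |
|---|---|---|
| 0.5 | 0.75 | 25% |
| 0.7 | 0.85 | 15% |
| 0.9 | 0.95 | 5% |
| 0.965 | 0.982 | 1.8% |

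At 0.5, 1/0.75 = 1.33, equivalent to 33% more subjects. The pairwise standard error, √(2/n × 2(1 − rho)) against √(2/n × (1 − rho²)), falls from 0.289 to 0.250 SD with 24 per arm and from 0.258 to 0.224 SD with 30 per arm. A three-visit model with baseline means constrained equal gives the same 25% and 5%, under compound symmetry and under AR(1) with the same baseline-to-post correlation.

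**4. Unequal SDs.** With k = SD post/SD baseline, the ratio is k²(1 − rho²)/(1 + k² − 2 × rho × k). The range of k is assumed. At rho = 0.5 the ratio is 0.571 for k = 0.8 (a 43% cut) and 0.871 for k = 1.2 (a 13% cut). At rho = 0.9 the cuts are about 39% and 2%.

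**5. Carryover contrast.** If correlations and SDs are equal across visits, baseline has zero covariance with the post-to-3-month change, so the cut is 0%.

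**6. Minimisation factors.** Simulation: 4 arms, N = 120, minimisation choosing the best arm with probability 0.8 (assumed), rho = 0.5, 8,000 runs per setting, Monte Carlo standard error about 0.24 points. The factors explain 0%, 15% or 30% of outcome variance equally at both visits (assumed).

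| Analysis | Type I error (0/15/30%) | Mean squared SE relative to change contrast |
|---|---|---|
| Change contrast | 4.7/5.3/4.9% | 1 |
| Baseline, no factors | 5.1/4.9/3.2% | 0.756/0.757/0.757 |
| Baseline and factors | 5.2/5.5/4.9% | 0.759/0.715/0.652 |

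A closed form agrees. With R the share explained, the correlation within factor strata is (rho − R)/(1 − R). At R = 0.15 this is 0.35/0.85 = 0.412, giving a ratio of 0.85 × (1 − 0.412²) = 0.706. At R = 0.30 it is 0.2/0.7 = 0.286, giving 0.7 × (1 − 0.286²) = 0.643. The simulated values are slightly higher because of the degrees of freedom spent.

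**The case against.** **The loss is conditional.** The plan lists no fixed effects, so a common-baseline model might have been fitted and would already recover the loss. That is right as far as it goes. But nothing in the document says so, and an unlisted best-fit search does not supply it.

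**25% may be too high.** The 0.5 is a planning input with no stated source. The only FMA-UE correlation quoted from data is the 0.965 test-retest value for "reliability in people with chronic stroke", which gives 1.8%. This stands as a limit on size. Test-retest agreement is, however, likely an upper limit for a correlation across eight weeks of differing treatments, and even at 0.9 the cut depends heavily on the SD ratio.

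**Last observation carried forward raises the correlation.** If all 20% dropout came before week 4, with equal SDs and no mean shift, the analysed correlation would be 0.8 × 0.5 + 0.2 = 0.6, and the cut (1 − 0.6)/2 = 20%. This is correct and lies within the range above; later dropout matters less.

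**The factors cause no defect in the change contrast.** Its simulated type I error stays near 5%. This also stands, and their prognostic strength is assumed. With R = 0.30 they would raise the total cut only from 5% to 7.1% at rho 0.9, and from 1.8% to 2.5% at 0.965. The main reason to include them is that the recommended post-baseline model becomes conservative without them if they are strongly prognostic.

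**The trial looks finished.** The text is in the past tense; the 120 subjects "were recruited from the local self-help groups" and their mean age is reported. That limits the remedy, as set out in the fix.

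**Conclusion.** The concern holds. As stated, the primary pre- to post-intervention analysis uses neither baseline FMA-UE as a covariate, nor a common-baseline constraint, nor the minimisation factors. With free group-by-visit means and equal SDs, the forgone variance reduction on that contrast is 25% at the plan's correlation of 0.5, 5% at 0.9 and 1.8% at 0.965. If 0.5 was meant as the adjacent-visit AR(1) correlation, the baseline-to-post correlation is 0.5² = 0.25 and the cut is 37.5%.

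These figures apply to the baseline-to-post contrast, not to the three-visit omnibus test or the carryover analysis. Validity is not in doubt: the change contrast keeps its type I error unless the minimisation factors predict change, and power meets the plan. The change should be made, with medium confidence in its size because the true correlation and SD ratio are unknown.

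**What to change.** State the fixed effects. The response is FMA-UE at the post-baseline visits, with group, visit, group-by-visit, baseline FMA-UE, baseline-by-visit, age band, sex, stroke type and side of lesion. An equivalent route keeps baseline as a response with its mean constrained equal across arms, with the same four factors. Treat each secondary outcome likewise, using its own baseline.

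The cost is no new data and about 6 degrees of freedom (baseline 1, age band 2, sex 1, stroke type 1, side 1) plus the baseline-by-visit terms, out of 120 subjects. If outcome data have already been analysed unblinded, keep the stated model as primary and report this one as a labelled sensitivity analysis. In that case the primary result itself gains no precision.

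### Heterogeneous AR(1) with no stated random subject effect does not match the constant 0.5 correlation used for sizing; under stated conditions the pre-to-post standard error is about 1.22 times too large

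*Combined protocol and SAP*

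**What the plan says.** The Design section sizes the trial with "correlation among measure of 0.5 and non-sphericity correlation of 1", that is, one correlation for every pair of visits. It concludes: "Ninety-six subjects were necessary to detect a significant between-group difference in the improvement of the upper limb motor control measured by FMA-UE". For 20% dropout it adds 24 subjects, giving 120 (30 per group).

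The Outcome Measure section lists five assessments, three of them from baseline to the end of treatment: baseline, week 4 and week 8.

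The Statistical Analysis section uses linear mixed models to "compare the changes over time in variables of interest between those in the Bi-TENS+TOT group and those in the Uni-TENS+TOT group", and likewise against the placebo and control groups. On the model it says "The maximum likelihood estimation was used to selected the best fit model" and then "The first-order autoregressive structure with heterogeneous variances (AR (1): heterogeneous) was used to estimate" the parameters. On the window it says "The intervention effect from pre-intervention to post-intervention was analyzed by LMM"; the same method serves for post-intervention to 3 months. Missing data are handled thus: "Intention-to-treat analysis (last observation carry forward) was used". Bonferroni-corrected post-hoc comparisons follow only a significant overall test.

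The section does not say whether week 4 enters the pre-to-post model, whether there is a random subject effect, or which candidate models were compared and by what criterion.

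**The concern.** Heterogeneous AR(1) lets the variance differ by visit but has one correlation parameter: r between adjacent visits and r² between visits two apart. With three visits and no random intercept, a correlation of 0.5 between adjacent visits forces 0.25 between baseline and week 8. The sizing assumed 0.5 for both. The two agree only if the correlation is 0 or 1.

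The pair of visits that AR(1) constrains this way is the pair that defines the pre-to-post change on FMA-UE, the primary outcome. If the fitted correlation for that pair is too low, the fitted variance of the change is too high, and a real difference between Bi-TENS+TOT and a comparator could be missed.

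**Working it through.** **Inputs.** From Design: d = 0.314, alpha 0.05, power 0.80, correlation ρ = 0.5, non-sphericity 1, four groups, N = 96 (24 per group) before dropout and 120 after. From Outcome Measure: three visits from baseline to week 8. My assumptions: f = d/2 = 0.157, two-sided contrasts, unit SD at each visit, and complete data unless stated.

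**1. Reproduce the plan's N.** For the within-between interaction with k = 4 groups and m = 3 visits:
- λ = f²·N·m/(1−ρ) = 0.157² × 96 × 3/0.5 = 14.20
- df1 = (k−1)(m−1) = 6; df2 = (N−k)(m−1) = 184
- Power = 0.803, and 96/(1−0.20) = 120.

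Two, four or five visits would need 116, 84 or 76. The three-visit reading is inferred from this match; the documents do not state it.

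**2. Pre-to-post contrast when the true correlation is constant at 0.5.**
- True variance of week 8 minus baseline: 2(1−ρ) = 1.0.
- The best-fitting heterogeneous AR(1) has r = 0.5 and equal SDs, so its variance is 2(1−ρ²) = 1.5.
- SE ratio = √[(1−ρ²)/(1−ρ)] = √(1+ρ) = √1.5 = 1.225. Simulation with 24 per group gave 1.21.
- At N = 96 (92 df) the critical value is in effect 1.986 × 1.225 = 2.432, so the type I error is 1.7%.
- Illustration: a raw effect of 0.817 SD has 80% power for one contrast at N = 96. The estimate is unchanged by the covariance, but the inflated SE cuts power to 66%. At N = 120 power goes from 88% to 77%.

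Baseline to week 4 and week 4 to week 8 have SE ratio 1.00.

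**3. Week 4 against the average of the two end visits.** With coefficients (1, −2, 1):
- True variance: 6 × (1−0.5) = 3.0.
- AR(1) variance: 6 + 2(−1 + 0.25 − 1) = 2.5.
- True/model = 1.20, so the type I error is 2[1 − Φ(1.96/√1.2)] = 7.4% (7.3% with t). AR(1) is anti-conservative here.

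**4. Overall 6-df group-by-time test.** Because steps 2 and 3 pull in opposite directions, its type I error stays at about 4 to 5%. Its power depends on the time pattern of the effect. Scaling each pattern to 80% under the correct covariance at N = 96:

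| Effect pattern | Power with AR(1) |
|---|---|
| Linear to week 8 | 60% |
| Early or late onset | 69% |
| Half the week-4 effect lost by week 8 | 80% |
| All of it lost by week 8 | 85% |

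**5. Sensitivity.**
- Constant correlation of 0.3, 0.7, 0.8 or 0.9: SE ratio 1.14, 1.30, 1.34 or 1.38. With the same raw effect at N = 96, the power loss shrinks at high correlation (95% to 85% at 0.7, 99% to 96% at 0.8).
- 120 randomised, 20% random dropout, last observation carried forward, correlation 0.5: SE ratio 1.18 to 1.25; contrast power 61–71% with AR(1) and 76–83% with unstructured, depending on dropout timing and effect pattern.
- Only baseline and week 8 modelled: ratio 1.00, because heterogeneous AR(1) with two visits is already unstructured.
- Random intercept included: ratio 1.00.

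**The case against.** The strongest reply is that no error in the plan has been shown. A sizing correlation is a simplification and need not equal the analysis covariance. If the 0.5 was meant for baseline to week 8, an adjacent-visit correlation of √0.5 = 0.71 satisfies AR(1) with no power loss. The documents give no observed FMA-UE correlations, and the test-retest value of 0.965 under Primary Outcome is not an eight-week correlation under treatment. All this stands.

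The best-fit sentence comes just before the AR(1) sentence and may mean that the covariance was chosen from the data. If it was, the misfit is unlikely: under constant 0.5, AR(1) beat heterogeneous compound symmetry on likelihood in 3–5% of simulated complete-data trials (4–14% with dropout and carry-forward). But no candidates or criterion are named, so a reader cannot tell.

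The 66% and 77% are also not the power of the plan's own tests. They concern one contrast that the plan did not size, without the overall-test gate or the Bonferroni correction. They show scale only.

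A reader might infer that a conservative error leaves any positive result safe. That is too strong: it holds for the pre-to-post contrast, but an overall test driven by a week-4 peak has no such protection. A reader might also carry the 1.22 into the follow-up window. There the visits are unequally spaced (week 8, 1 month, 3 months), and the figure transfers only if correlation is constant in that window too.

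**Conclusion.** The point holds conditionally. The named structure and the sizing assumption differ. If correlation is constant at 0.5, all three visits are modelled, no random intercept is present and AR(1) was not chosen by fit, the pre-to-post SE is about 1.22 times too large and the test of that contrast runs at about 1.7% instead of 5%. The overall test may gain or lose power.

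The documents do not support saying that the trial was analysed with a wrong covariance or that it lost 14 percentage points of power, because they establish none of the four conditions. If AR(1) is the true structure, its SE is correct; with adjacent correlation 0.5 the illustrative contrast then has 63% power at N=96 (73% at 120), which is a question of sizing that no change of covariance would repair.

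What is established is an under-described model with a restrictive structure where a safer one is available at little cost. It merits a change, but it is not a fatal fault.

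**What to change.** - Use an unstructured covariance over the visits in each window, with no random intercept added to it. It is valid whether correlation is constant or decays.
- Pre-state heterogeneous Toeplitz as the fallback for non-convergence; it contains both AR(1) and compound symmetry.
- State which visits and random effects enter each model, and which interval the sizing correlation of 0.5 refers to.
- The Subjects section already reports the recruited sample. If the analysis has been run, keep AR(1), state how it was selected, and report the unstructured fit beside it as a sensitivity analysis.

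Cost: some SAP wording, one extra model fit per outcome, and two more covariance parameters at three visits (6 against 4). When AR(1) was the true structure, simulated power was 0.610 with unstructured and 0.611 with AR(1) at N=96, and 0.743 and 0.745 at N=120.
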